Secondarily, the number of patients in each treatment group that experience persistence or recurrence to the degree that surgical evacuation is required will be compared. Patients who prospectively undergo middle meningeal artery embolization will be compared to retrospective matched controls of patients that underwent medical management. We hypothesize that patients who undergo MMA embolization as compared to simple observation alone will be less likely to ultimately need surgery and have a higher likelihood of SDH resolution after 90 days.

Specific Aim 2:

Determine the safety and efficacy of middle meningeal artery embolization for recurrent and refractory subdural hematomas after initial surgical evacuation.

MMA embolization has emerged as an adjunct treatment for patients who experience recurrent or refractory SDH after initial surgical evacuation. These patients will require surgical evacuation of the hematoma for their condition regardless of the use of MMA embolization. For patients with a residual SDH or who develop recurrent SDH within 30 days of initial standard of care surgery, the patients that have adjunct treatment with MMA embolization will be compared to historical patients that are managed with continued observation versus repeat surgery. We hypothesize that patients who undergo MMA embolization will have a higher likelihood of demonstrating radiographic improvement of the SDH and have a lower rate of requiring additional surgery.

Methodology

Participants

Approximately 200 patients with chronic subdural hematoma are treated at Barnes-Jewish Hospital annually. Patients aged 18+ of any race, sex, and socioeconomic status undergoing treatment for subdural hematoma will be identified by screening of the inpatient neurosurgical units or identification by an investigator. Patients will be approached regarding enrollment in the study at the time a decision is made to treat the subdural hematoma. If a patient expresses interest, an investigator or coordinator will provide the written consent form and explain the

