Patients 18 years or older who have undergone surgical evacuation of a subdural hematoma and have a significant residual hematoma status post-surgery or who develop a recurrent subdural hematoma.
2. Minimal symptoms such as headache, altered mental status, or mild neurological deficit only
3. Ability to understand and sign written informed consent by patient or LAR

If any of the following criteria are met, the individual will be excluded from participation:

1. Significant midline shift and/or neurologic symptoms requiring urgent decompression.
2. Common carotid stenosis of over 50%.
3. Significant contraindication to angiography (eg. kidney failure, difficult anatomy).

4. SDH related to underlying condition

Groups:

1. Embolization Only
 - a. Patients with new chronic or acute SDH with minimal symptoms only, or who are poor surgical candidates (dual antiplatelet therapy or systemic anticoagulation, ASA Class 4 or greater)
2. Embolization + Standard of Care Evacuation
 - a. Patients with chronic or acute SDH who failed conventional surgery at any point needing additional intervention, not requiring urgent evacuation
 - b. Recurrent SDH
3. Medical Management (Historical Cohort)
4. Surgery Alone (Historical Cohort)

Study Procedure

Middle meningeal artery embolization is ideal for patients with minimal symptoms or that are poor surgical candidates due to the need for continued anticoagulant or antiplatelet therapy. For patients who meet inclusion criteria, MMA embolization as an adjunct treatment will be offered. For patients that are medically managed, they will undergo MMA embolization to prevent growth or recurrence of the hematoma and have standard imaging follow up. For patients that require evacuation of the hematoma due to size or symptoms, they will undergo standard of care surgery via burr hole or craniotomy at the treating neurosurgeon's discretion and then at a later date during the same hospitalization receive MMA embolization. These patients may have already had multiple surgical evacuations with recurrence of the hematoma.

Once consented and enrolled, patients will undergo MMA embolization in the neuro-angiography suite via selective MMA catheterization and embolization with 150-250 micron polyvinyl alcohol (PVA) particles. The neurointerventional radiology department at BJH is a high volume center. Physicians and staff are experienced in neurovascular embolization for a variety of indications.

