The National Institutes of Health Stroke Scale (NIHSS) is an objective measure of impairment caused by a stroke. Eleven items are evaluated, with a potential score ranging from 0 to 42, with a higher score indicating more impairment.

Privacy/Data Protection

Patients will be assigned a unique study identification number at the time of consent. This number will link to identifying protected health information in a separate locked database accessible only to relevant research team members. Clinical study data will be entered into a secure database on RedCap under the study ID number to maintain patient data confidentiality.

Screening:

Study ID	MRN	Last Name	First Name	Admit Date	Enrolled Y/N	Date Consent Signed	Signed By Patient/ LAR	Exclusion

Initial Data:

Study ID	Birth Year	Sex	Race	(relevant comorbidities)	Use Anticoagulant y/n	Name of Med (aspirin, warfarin)	Procedure Date	Presenting neuro symptoms

Any neuro history	NIHSS Presentation	Baseline mRS	Size of SDH at Presentation	Laterality of SDH Left Right bilateral	Procedural Complications	

Follow up:

Study ID	Date of Follow Up	Time Point (30, 90 days)	NIHSS	mRS	Size of SDH at follow up	Neuro Deficit

Analysis

Endpoints

Two primary endpoints will be analyzed, related to the two main aims of the study. Aim 1 is to establish if middle meningeal artery embolization is more effective than observation alone at preventing recurrence of subdural hematoma. Aim 2 is to determine if adding on middle meningeal artery embolization reduces the need for further surgery in patients that initially undergo evacuation. The number of patients that experience a recurrent or refractory subdural hematoma will be compared, as well as the number of patients in each group that require surgery after undergoing embolization.

Primary Endpoints:

Recurrent or progressive SDH
Secondary surgical evacuation required

Secondary Endpoints:

Change in size of SDH at follow up
Procedure-related complications
New neuro deficit
NIHSS/mRS at follow-up intervals

Statistical Analysis

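### Aim 2 has no single analysis population: its 30-day frame is absent from the inclusion criterion and Group 2, so Group 2 and its historical controls may differ in disease stage, with no safeguard in the plan

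*Combined protocol and SAP*

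**What the plan says.** The sentence in Specific Aim 2 that sets up the comparison covers patients as follows: "For patients with a residual SDH or who develop recurrent SDH within 30 days of initial standard of care surgery". In the same sentence, those who receive embolization "will be compared to historical patients that are managed with continued observation versus repeat surgery". The heading of the aim refers to "recurrent and refractory subdural hematomas after initial surgical evacuation".

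The enrolment text is wider. The second branch of inclusion criterion 1 takes patients after evacuation who "have a significant residual hematoma status post-surgery or who develop a recurrent subdural hematoma", with no window. Under Groups, item 2a reads "Patients with chronic or acute SDH who failed conventional surgery at any point needing additional intervention, not requiring urgent evacuation", and item 2b is recurrent SDH without qualification. Study Procedure says of the patients who go to evacuation: "These patients may have already had multiple surgical evacuations with recurrence of the hematoma".

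The Endpoints section describes Aim 2 in yet another way: whether adding embolization "reduces the need for further surgery in patients that initially undergo evacuation".

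For the controls, Groups gives only a label, Surgery Alone (Historical Cohort). The Objective and the sample-size paragraph under Participants call the controls matched, but no matching variable is listed anywhere. Statistical Analysis compares the primary endpoints by simple t-test, with no covariates.

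**The concern.** With historical controls, comparability depends on how the two sides are selected. The risk of another evacuation plausibly depends on how many times surgery has already failed and how long ago it was done. If patients enter the embolized group under one definition and controls are drawn from charts under another, a difference in further surgery could reflect the mix of disease stages and not the procedure. Further surgery is the primary endpoint for Aim 2. A result obtained in this way would also not clearly answer the question that Aim 2 asks, because the document does not settle which patients the question concerns.

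**Working it through.** The point rests on the text and on no sample-size or power figure, so there is no planned number to reproduce.

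**Step 1. Set the definitions side by side.**

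| Place | Surgical failure required? | Time limit | Prior evacuations |
|---|---|---|---|
| Specific Aim 2, comparison sentence | Yes, residual or recurrent SDH | 30 days from initial surgery; clear for recurrence, unclear for residual SDH | No limit stated |
| Inclusion criterion 1, first branch | No, new diagnosis | None | Not mentioned |
| Inclusion criterion 1, second branch | Yes | None | No limit |
| Group 2a | Yes | Expressly none | No limit |
| Group 2b | Recurrence | None | No limit |
| Study Procedure, evacuation pathway | Not stated | None | Several allowed |
| Endpoints, Aim 2 | Not stated | None | Not stated |
| Surgery Alone historical cohort | Not stated | Not stated | Not stated |

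**Step 2. Try three patients against the definitions.**

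- Recurrence inside 30 days of the only evacuation: fits Aim 2, the inclusion criterion and Group 2.
- Third recurrence, eight months after the first evacuation: fits the inclusion criterion, Group 2 and Study Procedure, but lies outside the recurrence window in Aim 2.
- New diagnosis, evacuated because of size, embolized later in the same admission, no failure: fits the first inclusion branch, the evacuation pathway in Study Procedure, the title of Group 2 and the Endpoints wording. This patient fits neither 2a nor 2b, and fits Aim 2 only if residual SDH remains. Whether such a patient counts is unclear.

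**Step 3. Look for a safeguard.** Selection of controls: no stage, index date or limit on prior evacuations is given. Matching: asserted, with no variables. Analysis: t-test without adjustment or strata. Data: the Initial Data form has Any neuro history and Procedure Date, but no dedicated field for the number or dates of earlier evacuations. Data Points does provide for neurological history from the chart and, where relevant, a date of surgery.

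**Step 4. Illustrate the possible size.** All stage-specific values here are assumptions. Suppose that controls follow the Aim 2 frame with a further-surgery risk of 20%. That figure is borrowed from the sample-size paragraph, where it is one overall planning rate tied to no stage. Let a share *s* of Group 2 lie outside the frame with risk *q* without embolization, and let embolization have no effect. Then

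embolized rate = (1 − *s*) × 20% + *s* × *q*; spurious difference = embolized rate − 20%.

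| *s* | *q* | Embolized rate | Spurious difference |
|---|---|---|---|
| 40% | 10% | 0.6 × 20% + 0.4 × 10% = 16% | −4 points |
| 40% | 30% | 0.6 × 20% + 0.4 × 30% = 24% | +4 points |
| 60% | 10% | 0.4 × 20% + 0.6 × 10% = 14% | −6 points |
| 60% | 40% | 0.4 × 20% + 0.6 × 40% = 32% | +12 points |

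Over *s* from 20% to 60% and *q* from 10% to 40%, the range is −6 to +12 points. The planned difference is 20% − 5% = 15 points. If the controls were the wider group instead, the signs would reverse.

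**The case against.** The strongest reply is that the Aim 2 sentence places one frame over both sides. Read that way, it defines the analysis set, and broader enrolment alone creates no mismatch. Controls are also called matched, and stage could be one of the factors. Both points stand as far as they go. They mean that a mismatch is possible but not demonstrated. They do not supply a safeguard, because no text limits the Aim 2 analysis of Group 2 to that frame or names a matching factor.

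A reader might infer several stronger things that the documents do not support:

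- **That the two groups are at different stages.** The stage of the historical surgical cohort is never defined, so this cannot be shown.
- **That Aim 2 admits only early first failures.** The 30-day limit attaches most naturally to recurrence and may not cover residual SDH. Nothing says first failure: a patient evacuated more than once within 30 days of the initial surgery would still fit.
- **That Group 2 will contain uncomplicated first evacuations.** Items 2a and 2b do not cover them. Study Procedure and Endpoints are loose enough to raise the question, but no more.
- **That stages could not be separated afterwards.** The chart holds the history, and Data Points allows for its collection. What is missing is a dedicated field and a plan to use it.
- **That the bias has a known direction or size.** The figures above are assumptions, and opposing shifts could partly cancel.

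**Conclusion.** The point holds as an inconsistency in the definition of the Aim 2 population, joined to a control group whose entry rules are unstated. Late recurrences are inside Group 2 and outside the recurrence window in Aim 2; the place of residual SDH beyond 30 days and of first evacuations without failure is unclear. This is more than missing detail, because two people who each follow the protocol could select different populations for the two sides of a primary comparison. The consequence is conditional: the groups may differ in stage, and the plan neither prevents nor adjusts for it. The illustrated shifts show only that such a difference could be material against the planned effect. They depend on assumed stage risks and shares and on applying the overall planning rate to controls. The documents do not settle which window is right.

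**What to change.** Reconcile Specific Aim 2, the inclusion criterion, the Group 2 definition, Study Procedure and Endpoints into one stated Aim 2 analysis population. Say whether the 30-day limit covers residual as well as recurrent SDH, and whether a first evacuation without failure counts.

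Apply the same entry definition and the same index date to Group 2 and to its historical controls for the primary Aim 2 comparison. Enrolled patients outside that definition can stay in the study, analysed as separate strata against controls at the same stage.

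Add three dedicated fields to both the prospective form and the chart-review form: date of initial evacuation, date of last evacuation, and number of prior evacuations. Name them as matching or adjustment variables, and replace the unadjusted comparison with one that uses them.

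The cost is protocol wording and three items that the chart already holds. The drawback is that the primary Aim 2 set will be smaller than all of Group 2.

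### Aim 2 does not hold repeat evacuation the same in the embolized and control arms, so its effect cannot be separated from that of embolization

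*Combined protocol and SAP*

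**What the plan says.** The Aim 2 population is defined under Objective, Specific Aim 2: "For patients with a residual SDH or who develop recurrent SDH within 30 days of initial standard of care surgery". Both arms have therefore already had one operation.

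On the embolized side, the same paragraph says: "These patients will require surgical evacuation of the hematoma for their condition regardless of the use of MMA embolization". The Groups list names the arm "Embolization + Standard of Care Evacuation". Study Procedure says of patients whose hematoma needs evacuation that "they will undergo standard of care surgery via burr hole or craniotomy", with embolization following later in the same admission. However, the inclusion criteria also admit patients who have already been operated on and have a significant residual, and Group 2 covers patients who failed earlier surgery and do not need urgent evacuation. For some of these, the earlier operation could be the only evacuation.

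On the control side, Aim 2 says that "the patients that have adjunct treatment with MMA embolization will be compared to historical patients that are managed with continued observation versus repeat surgery". The Groups list gives the surgical comparator only as "Surgery Alone (Historical Cohort", and does not say whether each of these patients had a second operation. Group 3, the medically managed historical cohort, corresponds to the Aim 1 comparator. Nothing assigns post-operative observation to it.

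The Endpoints section restates the Aim 2 question as whether "adding on middle meningeal artery embolization reduces the need for further surgery in patients that initially undergo evacuation". Statistical Analysis compares the primary endpoints by t-test, with no stratification or adjustment. Controls are described as matched, but no matching variables are named.

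**The concern.** The effect of an added treatment can be read from a two-arm comparison only if the rest of the treatment is alike in both arms. Here the other treatment is a further evacuation for the residual or recurrent SDH. It plausibly bears on both outcomes that Aim 2 hypothesizes about: radiographic improvement and the need for additional surgery. If the share of patients re-evacuated differs between the arms, the difference in outcome is a blend of the two treatments' effects and of whatever led the historical clinicians to observe rather than re-operate.

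A larger sample does not remove this, because it changes what is estimated and not how precisely. Nor do correct event rules alone: with a common day 0 and a clear definition of an event, the background treatment could still differ.

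**Working it through.** **1. The passages side by side.**

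| Place | Further evacuation in the embolized arm | Further evacuation in the controls |
|---|---|---|
| Specific Aim 2 | Needed regardless of embolization | Some observed, some re-operated |
| Groups | Part of the arm's label | Surgery alone; second operation not stated |
| Inclusion criteria, Group 2 text | Possibly none for some patients with a residual | Not addressed |
| Statistical Analysis | Not used | Not used |

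If all Aim 2 patients need evacuation regardless, a control managed by observation is not their counterpart. If some do not, the embolized arm is mixed too. In neither case does the plan align the two arms.

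**2. Inputs from the documents.** The only rates are those in the sample-size paragraph: 20% needing surgery without embolization and 5% with it, a contrast of 20 − 5 = 15 points. The 20% is not described as a rate after repeat evacuation. The share of controls observed, the rates by evacuation status and the split of the 200 embolized patients and 400 controls between the aims are not given. The plan's figure of 124 patients is not an input here. (It does not reproduce: a pooled normal formula gives 76 per arm, 152 in total, at two-sided 0.05, and 22 per arm, 44 in total, at the printed 0.5. That is a separate matter.)

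**3. Formula, with embolization set to no effect.** Let f be the share of controls observed, r_o the event rate if observed and r_e the event rate if re-evacuated. If all embolized patients are re-evacuated:

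- control rate = f·r_o + (1 − f)·r_e
- embolized rate = r_e
- spurious difference = f·(r_o − r_e)

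If a share g of embolized patients is not re-evacuated and has the same underlying rate r_o, the difference becomes (f − g)·(r_o − r_e). It vanishes when f = g, and changes sign with either factor.

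**4. Numbers (assumed).** With r_e = 20% and g = 0, in percentage points (positive favours embolization):

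| r_o | f = 25% | f = 50% | f = 75% |
|---|---|---|---|
| 10% (observed controls milder) | −2.5 | −5 | −7.5 |
| 20% | 0 | 0 | 0 |
| 30% | 2.5 | 5 | 7.5 |
| 40% | 5 | 10 | 15 |

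**5. Sensitivity to the base rate.** With r_e = 5% and r_o = 20-40%, the range is 0.25 × 15 = 3.75 to 0.75 × 35 = 26.25 points. In that setting f = 50% with r_o = 35% gives 0.5 × 30 = 15 points, the planned contrast. The mechanism is the same, but the size depends wholly on the assumed rates.

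**The case against.** The strongest reply is that all Aim 2 patients, controls included, had the initial operation, and that the evacuation in the Group 2 label may be that operation. Aim 2 would then compare embolization with usual care, whether observation or re-operation, which is a legitimate pragmatic question. The point about the initial operation stands: the imbalance concerns only the further evacuation. The reading does not settle the matter. The Aim 2 paragraph speaks of evacuation still to come, and the Endpoints section asks for the effect of adding embolization, not of embolization against a mix of alternatives.

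A second reply is that the controls are "compared to historical patients that are managed with continued observation versus repeat surgery", where the word versus may name two separate comparators. That is possible, and no text says that they are pooled. But no separate analysis is planned either, and the plan should say which is meant.

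Three stronger readings are tempting, and the documents do not support them:

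- A reader might infer that every embolized patient is re-evacuated, so that the benefit of evacuation is credited to embolization. The inclusion criteria leave room for embolized patients with no second evacuation, and observed controls may be milder cases, so the sign is open.
- A reader might infer that radiographic improvement would appear even if embolization did nothing. That depends on the baseline scan. The schedule takes a head CT before the procedure, which may follow the evacuation, while the data tables record size at presentation.
- A reader might infer that the whole planned effect is likely to be artefact. The 15-point figure is one corner of an assumed range.

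**Conclusion.** The concern holds in a limited form. Aim 2 does not fix evacuation status in either arm, its passages conflict on who is re-evacuated, and the planned test makes no allowance for it. The add-on effect that the plan asks for is therefore not isolated, and the direction of the bias is unknown.

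The illustrative size is from 7.5 points against embolization to 15 points in its favour. It assumes no embolization effect, all embolized patients re-evacuated, 20% events after re-evacuation, 10-40% if observed, and 25-75% of controls observed. None of these is given in the documents as a value for the Aim 2 strata. The finding rests on the text, not on these numbers. It should be resolved before the Aim 2 comparison is run, because it decides what that comparison estimates.

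**What to change.** 1. Reconcile Specific Aim 2, the inclusion criteria, Groups and Study Procedure on who belongs in each Aim 2 arm. Which definition applies is for the investigators to decide.
2. For every embolized and control patient, abstract whether re-evacuation was part of the management chosen when the residual or recurrent SDH was identified. Use that moment as a common time zero, and count any evacuation beyond that chosen management as an endpoint event. This rule is essential because repeat surgery is both a control treatment and a primary endpoint.
3. Compare embolized and control patients only within the same evacuation status: re-evacuated with re-evacuated, and not re-evacuated with not re-evacuated. Make a stratum-weighted estimate, for example Mantel-Haenszel, the Aim 2 primary result, and report each stratum descriptively.
4. Measure radiographic change from the same point relative to evacuation in both arms.

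The cost is one more abstracted field, text changes and some precision. Data Points already records the date of surgery where relevant, but the data tables have no field for index re-evacuation. Individual strata may be thin. At two-sided 0.05, power for 5% against 20% is about 72% with an assumed 50 embolized and 100 controls, and about 38% with 25 and 50, which is why the combined estimate should be primary. No additional patients or procedures are needed. Stratifying removes only the imbalance in evacuation; differences in severity between prospective patients and historical controls within a stratum remain.
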